IRB Amendment (#9072)	Modification to reconsent process and new consent capacity assessment tool. Variable added in the demographic questionnaire. Gift cards for less than \$40 can be given to those who don't want to share their SS#. COVID-19 procedures for re-engaging in research.	7/14/2020
IRB Amendment (#8975)	All research interactions and recruitment on HOLD due to COVID. Participant notification postcard approved.	3/25/2020
IRB Amendment (#8957)	COVID-19 related: Month 6 can occur up to Month 10	3/20/2020
IRB Amendment (#8887)	Approval to work with Promotions Office to create a recruitment video. Additional recruitment materials include TV slide, brochures. Added Danbury as research location.	2/18/2020
IRB Amendment (#8865)	Add [name] and remove [name]	2/6/2020
IRB Amendment (#8829)	IC version 7; addition of Jennings at Garfield and Jennings at Brecksville	1/28/2020
IRB Amendment (#8761)	Add [name]; Recruitment materials V 4.0	1/02/2020
IRB Amendment (#8741)	Remove [name]	12/10/2019
IRB Amendment (#8566)	Add [name] and [name]; Add Park Village Pines; Researchers can verify participant activities with caregiver; Revised IC V6.0	9/20/2019
IRB Amendment (#8552)	Revised IC V5.0; Change in randomization; waiver of documentation of consent in specific circumstances.	9/9/2019
IRB Amendment (#8428)	Transition of study to Revised Common Rule; added retention plan V1; Revised IC V4.0	7/19/2019

IRB Amendment (#8332)	Add [name] & [name]; Revised protocol v4.1; Reading screening form v2.0 5/13/19; Community presentation, v1 5/20/19; Wayfinding brochure for staff, v2 5/22/19; inclusion of 3 additional sites; DSMP, v2.0	5/24/2019
IRB Amendment (#8319)	Adapted Recruitment Materials V3 dated 5/16/19	5/24/2019
IRB Amendment (#8287)	Add GR data collectors, revised recruitment and intervention, revised continuing assent script and SR CRF, research handout of center staff	5/7/2019
IRB Amendment (#8097)	Revised protocol V 2.1; Revised ICF V 2.1 dated 11/6/2018; Updates to informed consent process; Updates to data collection process; Use of REDCap	2/22/2019
IRB Continuing Review (#7787)		11/5/2018
IRB Amendment (#7787)	Add [name] & [name]; Revised Inclusion criteria; Additional document revisions	9/13/2018
IRB Amendment (#7750)	Add [name]	8/24/2018
IRB Amendment (#7546)	Concordance review for protocol and grant	5/24/2018
IRB Initial Submission (#1052)		12/14/2017
IRB New Project (#7169)		12/3/1207

## 6. Purpose of Research

The overall goal of this project is to assess the contribution of cues and spaced retrieval education on wayfinding ability and life space in persons with wayfinding impairment who live in long term care communities in a randomized controlled trial. We will select nine senior assisted living residences and recruit 137 residents identified as having wayfinding problems who can move themselves and communicate. We will randomize the facilities to one of three arms 1) Control (no changes); 2) Cued (salient environmental landmarks and signage placed at key decision points) plus staff training on use of the cues and 3) Cued plus Spaced- Retrieval education. Subject characteristics including mobility, demographic variables, activities of daily living, and cognitive ability will be measured along with life space mobility (spatial extent of mobility). We will test all subjects' wayfinding ability (primary outcome) and life space (secondary outcome) at baseline and at 1, 3, 6, and 12, months. We will compare wayfinding performance over time among the 3 trial arms.

The specific aims are:

Aim 1: To examine the effect of salient cues with and without spaced retrieval education on wayfinding ability initially and over time in older adults who have wayfinding deficits in long term care communities. HO1: Subjects will have improved wayfinding (faster, more accurate) in the cued condition versus the control condition at months 1, 3, 6, and 12; and post intervention compared to pre intervention.

H02: Subjects in the cued condition + Spaced Retrieval education will have improved wayfinding ability compared to the control and cue alone condition at times 1, 3, 6, and 12 months.

Aim 2: To determine the effects of salient visual cues and spaced retrieval training on life space.

H03: Subjects in the cued conditions will have larger life spaces than those in the control condition at times 1,3, 6 and 12 months.

H04: Wayfinding ability will be positively correlated with larger life space over time.

Exploratory Aim 3: To determine which subject characteristics are most amenable to the intervention; and which subject characteristics place persons at risk for less responsiveness to the intervention so that the intervention can be appropriately targeted.

The significance and innovation of this project is that it may provide one of the first research supported nonpharmacological interventions for the problem of wayfinding for persons in existing long term care communities.

## 7. Subject Population Description

### 7a. Subject Population description

**Please enter the anticipated number of subjects.**

137

**Please provide justification for why the number of subjects to be recruited is appropriate.**

The sample size for this study was determined based on Specific Aim 1, Hypotheses H01 and H02 for the pairwise comparisons of the trial arms. In the prior R15-funded study of the PI, the effect size for the difference in wayfinding time observed under cue versus no cue condition was 0.42 (a reduction of 8 minutes on average, with a standard deviation of 19 minutes). In the proposed study, wayfinding will be measured at baseline, 1, 3, 6, and 12 months. Since baseline measure will be used as a covariate in the analysis of repeated measures of outcomes (see the analysis section), the adjusted standard deviation in this analysis would be smaller than unadjusted. Assuming correlation of 0.4 between pairs of repeated measures, the effect size adjusted for the design of the proposed trial and analysis strategy is 0.67, which would be detected with power 0.8 or greater in two-sided tests using 0.05 level of significance with the sample size of 36 per group. Next, this sample size was adjusted to account for clustering of participants within care communities using a conservative estimate of the intraclass correlation coefficient (ICC) of 0.0012. The resulting design effect factor is 1.042 yields the sample size requirement of 38 per group, or 114 total. Finally, to account for projected 20% attrition, 137 participants will need to be recruited. This corresponds to the average recruitment goal of 11 participants per care community. The participating care communities stated that they have 10 to 30 available participants satisfying the inclusion criteria; therefore the required sample size is feasible.

**Briefly describe the subject population characteristics (i.e., age ranges, and where appropriate, gender, ethnic background, and health status).**

Planned enrollment includes men and women 62 years and older. For NIH our enrollment table includes an ethnic and racial mix of subjects in alignment with the population in the cities in which the study is being conducted - however, the sample is a convenience sample.

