**Specific Aim 1** examines the effect of salient cues with and without spaced retrieval education on wayfinding ability. The statistical model #1 for the repeated measures of wayfinding ability at 1, 3, 6, and 12 months will include the following explanatory variables: wayfinding ability at baseline, time (with levels 1, 3, 6, 12 months), trial arm, and control variables measured at baseline (see the measures section). Time will be included as categorical variable with the above mentioned levels to model potentially non-linear (polygonal) changes in outcomes over time. For the first measure of wayfinding ability, average speed calculated as described in the measures section, this model will be implemented as a linear mixed effects (LME). It will also include random effect indicating facility as will all other statistical models. The LME model generalizes classical analysis of repeated measures and allows for data missing at random, time-varying covariates, and structured covariance matrix. The participants who completed at least one post-baseline assessment will be included in the analysis following the intent to treat principle. The second measure of wayfinding ability, the proportion of wrong turns, by definition takes values from the [0, 1] interval and will be analyzed using generalized LME with beta distributed errors. Beta distribution supported on [0, 1] interval is particularly suitable to this measure.

The essential parameter of interest in the statistical model #1 is associated with the trial arm variable. The least square (LS) means corresponding to this variable will be output from the model, and differences among them will be tested. The test of significance of the differences between LS means for cues versus control and cues + spaced retrieval education versus control will yield the formal test of hypothesis H01. The test of the significance of the differences between cues + spaced retrieval education versus cues alone will yield the formal test of hypothesis H02. After testing the main trial arm effects, time by trial arm interaction will be added to the statistical models to explore whether intervention effects change as time progresses. The significance of the interaction term will be assessed, and differences in LS means by trial arm at each time point will be tested to determine the immediate and sustained effects.

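### The sample-size paragraph has two arithmetic slips that offset at the stated ICC, and its power figure makes no allowance for having only four facilities per arm

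*Protocol*

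**What the plan says.** Protocol section 7a sizes the trial on H01 and H02, the pairwise arm comparisons. An unadjusted effect of 0.42 becomes 0.67 after allowing for the baseline covariate and the repeated measures (correlation 0.4). The paragraph claims "power 0.8 or greater in two-sided tests using 0.05 level of significance with the sample size of 36 per group".

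It then adjusts for clustering "using a conservative estimate of the intraclass correlation coefficient (ICC) of 0.0012" and continues: "The resulting design effect factor is 1.042 yields the sample size requirement of 38 per group, or 114 total". The last step is attrition: "Finally, to account for projected 20% attrition, 137 participants will need to be recruited". It adds: "This corresponds to the average recruitment goal of 11 participants per care community".

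The SAP (Preliminary analysis) says that facilities are randomized and individuals analysed. Under Specific Aim 1, all arm contrasts come from one model: "The least square (LS) means corresponding to this variable will be output from the model, and differences among them will be tested". On clustering: "It will also include random effect indicating facility as will all other statistical models". On partial follow-up: "The participants who completed at least one post-baseline assessment will be included in the analysis following the intent to treat principle". No df method is named.

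On the number of facilities, Protocol section 6 says nine. Sections 8a (recruitment and inclusion criteria), 8b and 8d say 12.

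**The concern.** Each link in this chain is stated with its inputs, so each can be checked, and two do not follow. An attrition allowance should divide by the retained fraction; here the target was multiplied by 1.2. A design effect should use the number of participants per cluster; the printed value does not match the stated ICC and cluster size.

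The third issue carries more weight. Arm varies only between facilities, so the precision of an arm contrast depends on how well the between-facility variance is known. With four facilities per arm it is known poorly. A design effect enlarges the variance but does not account for the wider t reference distribution that few clusters require. The SAP describes the LS-mean contrasts as the formal tests of H01 and H02, so the choice of df affects both the planned power and the p-values that will be reported.

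**Working it through.** **Inputs.** From Protocol section 7a: effect 0.42 unadjusted and 0.67 adjusted, correlation 0.4, two-sided 0.05, 36 per group, ICC 0.0012, design effect 1.042, 38 per group (114), 20% attrition, 137 recruited, 11 per community. From sections 8a, 8b and 8d: 12 facilities. The documents give three arms. Four facilities per arm is 12/3.

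**1. Reproducing the plan's chain**
- Variance factor for the mean of four post-baseline measures adjusted for baseline: (1 + 3 × 0.4)/4 − 0.4² = 0.39. Then 0.42/√0.39 = 0.673, stated as 0.67.
- Two-sample t-test, effect 0.67, 36 per group, 70 df: power 0.8005. The 36 is therefore an individual-level figure.
- 36 × 1.042 = 37.5, so 38 per group and 114 in total.
- 114 × 1.2 = 136.8, so 137.

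**2. Attrition**
- 137 × 0.8 = 109.6, or 36.5 per arm.
- 137 retains 114 only if the loss is at most 1 − 114/137 = 16.8%.
- Keeping 114 would take 114/0.8 = 142.5, so 143.

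**3. Design effect, 1 + (m − 1) × ICC**
- Stated inputs: 1 + 10 × 0.0012 = 1.012.
- 1.042 arises as 1 + 35 × 0.0012 (a cluster of 36, the arm size) or as 1 + 10 × 0.0042 (a different ICC). The documents do not show which.
- With 1.012: 36 × 1.012 = 36.4, so 37 per group and 111 in total; 111/0.8 = 138.75, so 139 recruits.

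**4. The two slips together, individual-level df**
- With 109.6 completers in 12 facilities, m = 9.13 and the design effect at ICC 0.0012 is 1.0098. The need is 36 × 1.0098 = 36.35 per arm, against 36.53 available. Power is 0.803.
- If the ICC is 0.0042, the design effect is 1.0342 and power is 0.793.

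**5. Power on between-facility df**

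Noncentral t, two-sided 0.05, noncentrality 0.67 × √(n/(2 × DE)), with n = N/3, m = N/12, DE = 1 + (m − 1) × ICC and df = 12 − 3 = 9:

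| Fully followed N | ICC 0.0012 | ICC 0.0042 |
|---|---|---|
| 109.6 (all 20% give no post-baseline data) | 0.718 | 0.708 |
| 114 | 0.73 | 0.72 |
| 137 (no loss) | 0.808 | 0.796 |

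At ICC 0.0012, power of 0.80 needs about 135 fully followed participants (root 134.2). The effect detectable with 0.80 power is 0.74 at N = 109.6 and 0.66 at N = 137, against the planned 0.67.

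**6. Facility count.** 137/12 = 11.4 agrees with the stated 11 per community; 137/9 = 15.2 does not. Nine facilities would leave 9 − 3 = 6 df, with power about 0.66 at 109.6 completers and ICC 0.0012.

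**The case against.** A reader might infer from the 70-df match that the plan ignores clustering. It does not. Section 7a gives the 0.8 as an explicit step before clustering and inflates the sample size in the next sentence, and the SAP puts a facility random effect in every model. What is missing is narrower: a df method, and an allowance for few facilities.

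A reader might also infer that the attrition slip leaves the trial short by six recruits. That treats 143 as the correct target, but 143 rests on 114, which contains the unexplained 1.042. With the design effect that the stated inputs give, the target is 111 and the recruits 139. The design-effect slip is in the safe direction, and at ICC 0.0012 it absorbs the attrition slip.

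The low end of 0.72 is an extreme, because the SAP keeps anyone with one post-baseline visit. As an illustration on an assumed pattern, 5% lost before each of the four visits gives an effective N of about 124 and 9-df power of about 0.77 (0.76 at ICC 0.0042). The other baseline covariates may add precision, and the documents give no figure for that gain. If the estimated facility variance is near zero, some df methods may also return more than 9 df.

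Finally, section 8d calls this a pilot RCT with feasibility foremost, and the amendments show sites already closed out, so restating power changes no design decision. These points lower the stakes. They do not remove the two wrong figures, the power claim for H01 and H02, or the open df choice.

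**Conclusion.** Two figures in section 7a are wrong as written: 137 does not retain 114 after 20% attrition, and 1.042 does not follow from ICC 0.0012 with 11 per community. Together they cost almost nothing: individual-level power stays at 0.803, or 0.793 if the ICC is 0.0042.

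The power statement is unsupported in one further respect. It rests on individual-level df and makes no allowance for four facilities per arm. On 9 df, power is about 0.72 to 0.81 at ICC 0.0012 and 0.71 to 0.80 at ICC 0.0042, with partial completers placing it inside those ends. The upper end is reached only with almost no loss of data.

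These figures assume 12 facilities split equally, effect 0.67, between-facility df, and no gain from the other covariates. The documents do not support saying that power is 0.72, that clustering was overlooked, or that more participants are required. The conflict between nine and 12 facilities is a separate editorial item, but that count sets the df. The whole point should be fixed; it is not critical.

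**What to change.** 1. In Protocol section 7a, reconcile 1.042 with the ICC and the cluster size actually intended.
2. State that 137 recruited yields about 110 completers at 20% attrition. Mention 143 only if 114 stays the target; with a design effect of 1.012 the target is 111 and the figure is 139.
3. In the SAP under Specific Aim 1, name a small-cluster df method for the arm contrasts, for example Kenward-Roger or between-facility df.
4. Restate power on that basis as a range: about 0.72 to 0.81 with 12 facilities at ICC 0.0012 (0.71 to 0.80 if the ICC proves to be 0.0042), with the assumption about partial follow-up written out.
5. Reconcile the nine facilities in Protocol section 6 with the 12 in sections 8a, 8b and 8d.

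The cost is a reworded protocol paragraph, one number in section 6 and one SAP line. No enrolment is added. The downside is that the stated power becomes somewhat less favourable.

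### The recruitment target of 137 does not cover the 20% attrition it is said to cover: it leaves about 110 of the required 114 (minor)

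*Protocol*

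**What the plan says.** The sample size justification in protocol section 7a works in four steps.

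1. It takes an unadjusted effect size of 0.42 (8 minutes over a standard deviation of 19 minutes) and, "Assuming correlation of 0.4 between pairs of repeated measures", concludes that "the effect size adjusted for the design of the proposed trial and analysis strategy is 0.67".
2. That effect is one "which would be detected with power 0.8 or greater in two-sided tests using 0.05 level of significance with the sample size of 36 per group".
3. It adjusts for clustering "using a conservative estimate of the intraclass correlation coefficient (ICC) of 0.0012". The stated design effect is 1.042, which takes 36 per group to 38 per group, 114 in total.
4. It closes with the attrition step: "Finally, to account for projected 20% attrition, 137 participants will need to be recruited".

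The same total appears in protocol section 6, where the plan is to "recruit 137 residents identified as having wayfinding problems", and as the entry for the anticipated number of subjects at the start of section 7a. Section 7a gives no time point for the 20% and no formula for the allowance. The SAP contains no sample size calculation of its own. Under Specific Aim 1, the SAP brings into the analysis everyone with one or more assessments after baseline.

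**The concern.** To end with a given number after losing a fifth of those recruited, the number has to be divided by 0.8. Adding a fifth to it is not enough, because the loss is then taken from the larger, inflated number. The step from 114 to 137 looks like the addition.

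Section 7a is the protocol's formal justification for the number enrolled. A reader would take from it that a 20% loss is fully absorbed, and on the stated figures it is not. The protocol also tracks attrition as a feasibility measure, so the planned allowance is the natural benchmark for the loss actually seen. That allowance should be stated correctly.

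**Working it through.** **Inputs, all from protocol section 7a:** unadjusted effect size 0.42; correlation 0.4; four post-baseline visits; two-sided alpha 0.05; power 0.8; 36 per group; ICC 0.0012; design effect 1.042; 38 per group and 114 total; attrition 20%; target 137.

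**Reproducing the plan up to the attrition step**

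- Effect size, averaging four visits with baseline as covariate: 0.42 / sqrt((1 + 3 x 0.4)/4 - 0.4^2) = 0.42 / sqrt(0.39) = 0.6725. Stated 0.67.
- Per group, two-sample t-test at d = 0.67: 35.96, so 36, with power 0.8005. Matches.
- Design effect: 1 + (36 - 1) x 0.0012 = 1.042. Matches. The cluster size used here is the arm size.
- 36 x 1.042 = 37.5, so 38 per group; 3 x 38 = 114. Matches.

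**The attrition step**

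- 114 x 1.2 = 136.8, which rounds to 137. This gives the stated figure; the factor 1.2 is inferred.
- 114 / (1 - 0.20) = 142.5, so 143 (48 per arm, 144, if arms are equal). This does not give the stated figure.
- Retained from 137: 137 x 0.8 = 109.6, or 36.53 per arm. Shortfall: 114 - 109.6 = 4.4.
- Retained from 143: 143 x 0.8 = 114.4.
- Attrition that 137 does cover: 1 - 114/137 = 16.8%.
- Gap in recruits: 143 - 137 = 6, and 6/143 = 4.2%.

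**Size of the effect on power**

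Two-sided t-test, alpha 0.05, d = 0.67, effective n per arm = n / design effect, degrees of freedom = 2 x effective n - 2.

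| n per arm | Design effect | Power |
|---|---|---|
| 38 | 1.042 | 0.806 |
| 36.53 | 1.042 | 0.790 |
| 36.53 | 1.012 | 0.802 |

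The last row uses the design effect for the 11 participants per community given in section 7a: 1 + 10 x 0.0012 = 1.012. The 36.53 rows assume that dropouts contribute nothing. All three rows treat participants as the unit of the test and make no allowance for the small number of randomised communities. They serve only to size the attrition step.

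**If dropouts contribute what they provided**

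The documents do not say when losses occur, so this is an illustration. Assume that the 20% loss is proportional to time over 12 months, with equal correlation of 0.4 and baseline as covariate.

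- The variance of the mean of k visits is (1 + 0.4(k - 1))/k - 0.16 = 0.84, 0.54, 0.44 and 0.39 for k = 1 to 4. The information relative to a completer is therefore 0.464, 0.722, 0.886 and 1.
- The loss splits 1:2:3:6 over the intervals ending at months 1, 3, 6 and 12. The shares with 1, 2 and 3 visits are then 3.33%, 5% and 10%, with 80% complete.
- Effective number per arm: 137/3 = 45.67, and 45.67 x (0.80 + 0.0333 x 0.464 + 0.05 x 0.722 + 0.10 x 0.886) = 42.9, above 38.
- Number analysed: 137 x (1 - 0.20/12) = 134.7.

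The range per arm therefore runs from 36.5 (dropouts give nothing) to about 42.9 complete-participant equivalents under this assumption.

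**The case against.** The best case for leaving the figure alone has three parts.

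*Partial completers are analysed.* Under the SAP, only people lost before their first post-baseline visit drop out of the analysis altogether. The full shortfall of 4.4 thus arises only if every loss comes before month 1. This stands as a limit on the consequence. It does not make the sentence right: section 7a presents 137 as the number that offsets a 20% loss from 114 and takes no credit for partial data. The 0.67 behind the 114 also reproduces only when all four post-baseline visits are available.

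*Another step errs in the opposite direction.* The 1.042 uses the arm size. With 11 per community the factor is 1.012, and 108 x 1.012/0.8 = 136.6, so 137 (or 139 if each arm is first rounded up to 37: 111/0.8 = 138.75). This also stands, and it means that 143 follows only while 1.042 is kept. Still, section 7a states 1.042, 38 and 114, and 137 does not follow from those.

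*Rounding contributes.* Without rounding up per arm the requirement is 36 x 1.042 x 3 = 112.5. Then 112.5/0.8 = 140.7, so 141, and the shortfall is 2.9. The gap narrows but does not close, and the protocol gives 114 as its requirement.

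A reader might go further and infer that the trial is underpowered because of this slip, or that recruitment has to rise. The documents support neither. The cost is under two percentage points in the worst case and may be nil. A reader might also take the 110 to be the number remaining at 12 months. That is plausible for a year-long study, but section 7a attaches no time point to the 20%.

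**Conclusion.** The point holds as a minor numerical inconsistency. On the stated requirement of 114 and the stated 20% attrition, 137 recruits leave 109.6. The matching recruitment figure is 143 (144 with equal arms), and the matching attrition for 137 is 16.8%. No other part of the protocol or SAP defines the allowance in a way that reconciles the three numbers.

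The worst-case cost is 0.806 - 0.790 = 0.016 in power, assuming that dropouts contribute nothing, that the design effect is 1.042, and that an individual-level t-test is used. It is smaller once partial completers are counted. The arithmetic of the shortfall rests on no assumption outside section 7a; only the explanation that 20% was added to 114 is inferred. The power figures are not an assurance of the trial's power and should not be carried into the protocol.

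**What to change.** Restate the end of the justification in section 7a so that 114, the attrition rate and the recruitment total agree. There are two ways to do so.

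- **Keep 137.** State that it allows for about 17% attrition. Alternatively, keep 20% and state that it leaves about 110 participants (36 to 37 per arm), slightly below 114, with participants who have some post-baseline data still contributing. The cost is one sentence, with no change to design, analysis or recruitment.
- **Hold to 114 retained at 20% attrition.** State 143 (144 with equal arms), and change the total in section 6 and the anticipated number in section 7a to match. The cost is three edits and six or seven more recruits.

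The choice depends on whether 114 is meant as a number to be retained, which the protocol should say. If 20% is kept, it should also give the time point to which the rate applies.
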